Monitoring mental health and safety. At each assessment visit, participants will complete the BDI to assess for depressive symptom severity. Any participant who endorses clinical levels of any psychiatric disorder or who endorses suicidality will be referred to [name] (a licensed psychologist), for further follow-up assessment. The psychologist will then provide a recommendation regarding the appropriate course of follow-up and also advise on whether it is safe for the participant to continue in the study. If a participant is found to be actively suicidal with a plan and/or intent, they will be escorted immediately to the emergency room at the Shands Hospital at the University of Florida. If safety is an issue, UF security or local authorities will be called for assistance. If a participant endorses suicidal thoughts or significant psychopathology, participants will be referred to [name] for further evaluation. Based on this evaluation, he will recommend follow-up assessment and treatment appropriate to the situation including treatment at the Psychology and/or Psychiatry Clinics within Shands Hospital at the University of Florida.

Adverse Event Reporting. An **adverse event (AE)** is defined as any unfavorable and unintended sign (including an abnormal laboratory finding), symptom, or disease temporally associated with the intervention irrespective of whether it is considered related to the intervention.

Non serious adverse events. Defined as conditions that may be unpleasant and bothersome to the participant that does not require discontinuing the study.

Serious adverse events (SAEs). Defined as events that may be harmful to the participant and/or may be serious enough to warrant either temporary or permanent discontinuation of the study intervention, either because they are intolerable or because they are judged to be potentially harmful. All serious adverse events require immediate reporting and an assessment of the implications for the continuation of the study and/or modification of the consent form. The following are considered serious events:

- It is acute or life threatening;
- It results in prolonged, permanent or severe disability;
- It is another severe illness including worsening of a pre-existing condition, injury or accidents;
- It is an inpatient hospitalization or surgical procedure, or a treatment to prevent a serious event;
- It results in death;
- It is a clinically significant abnormal laboratory or diagnostic test.

Table 3. Adverse Event (AE) Classification

Adverse Event (AE) Classification	
Definite.	Temporal pattern + known or expected AE response pattern + confirmed by stopping the intervention + reappearance of AE on re-challenge
Probable.	Temporal pattern + known or expected AE response pattern + confirmed by stopping the intervention + could not be explained by participant's clinical state
Possible.	Temporal pattern + known or expected AE response pattern + could have been produced by a number of other factors
Unknown.	Relationship for which no evaluation can be made
Not related.	AE for which sufficient information exists to indicate that the cause is unrelated to the study intervention

Classification of AE severity. The principal investigator will evaluate adverse events for seriousness, expectedness, severity, and relationship to study intervention at each study visit. The primary mechanism for ensuring participant safety will be clinical observation of symptoms. The study will be conducted and supervised by trained study staff and will monitor potential adverse experiences and symptoms. During each visit, participants will log any health-related problems or symptoms they are experiencing. These sheets will be reviewed by study staff before allowing the participant to continue. Community health services will be contacted immediately if warranted by the participants' symptoms.

All adverse events (AEs) will also be categorized according to the likelihood that they are related to the study intervention. Specifically, they will be labeled either definitely, probably, possibly or unrelated to the study intervention. The classification of potential relationship to the intervention is shown in Table 3.

Effective screening will exclude individuals who would be at increased medical risk as a result of participation in this research. FMRI contraindications, such as claustrophobia or some metal implants will be assessed by telephone screening and again on the day of the scan. [name], who has completed MRI safety training and has over 10 years' experience screening FMRI participants, will supervise these procedures. The RA who will conduct neuroimaging analyses will be trained in UF AMRIS safety procedures and will also be responsible insuring for participant safety. Adverse events, although unlikely, may occur as a result of neuroimaging. Such events will immediately be reported by [name] (PI) to the local IRB, with serious adverse events reported to both the IRB and NIH.

SAE reporting. Serious adverse events (SAEs) that are unanticipated, serious, and possibly related to the study intervention will be reported within 24 hours of study's knowledge of the SAE to the IRB in accordance with the regulatory requirements. Anticipated SAEs or those unrelated to the study intervention will be reported to the same individuals/entities in accordance with regulatory requirements.

Minor events will be reported to the IRB at the time of annual review. Both the principal investigator and the study staff will review the study weekly and examine reports of adverse incidents and reports of study participant recruitment and follow-up. Throughout the course of the study, information regarding issues deemed critical to the

study or to the safety of research participants will be provided to the principal investigator and other study investigators as needed. As a result of receiving this critical information, a meeting to discuss this information may be convened. Information deemed critical would include:

- serious and non-serious adverse events that may occur;
- suspicion of scientific fraud or misconduct;
- any other issues which may warrant protocol changes or modifications.

Adverse event (AE) and serious adverse event (SAE) determination and monitoring will be achieved via administration of structured questionnaires. Standardized forms for referring and treating study participants who experience adverse events will be in place.

Documentation of Training on Protection of Human Participants. All key personnel on the study have successfully completed good clinical practice training.

8. Possible Benefits:

There are well-documented benefits for older adults who participate in cognitive training, including improvement in working memory, attention, and executive functions. Deficits in these cognitive abilities significantly impact quality of life, financial capacity, medication adherence, and mortality in older adults. All participants undergoing CT may benefit from these effects. Those participants randomly assigned to the active tDCS+CT treatment group may experience further benefit beyond that of cognitive training alone. Benefits to society will include the contribution of novel data regarding the efficacy of neuromodulation methods for enhancing cognitive training effects in older adults. This may help inform treatment protocols in a growing segment of the US population (i.e., those 65 years and older). Data collected from this study will serve as a foundation for larger clinical studies that examine optimized methods for treating aging-related cognitive decline using cognitive training and tDCS. Some participants may not benefit from the study at all.

9. Conflict of Interest:

None

References:

3. Edden RA, Muthukumaraswamy SD, Freeman TC, Singh KD. Orientation discrimination performance is predicted by GABA concentration and gamma

oscillation frequency in human primary visual cortex. *J Neurosci*. Dec 16 2009;29(50):15721-15726.

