SMART Stimulation: Precision Neuromodulation of Cognition in Older Adults
NCT05377411
Document Date: 9/19/2023

Protocol # 202100953

1. Project Title

SMART Stimulation Study: Precision Neuromodulation of Cognition in Older Adults

2. Investigator(s):

[name]
[name]
[name]
[name]
[name]

Staff

[name] M.Sc.: Study Coordinator
[name], B.S.
[name], B.S.
[name], M.S.
[name], B.S.
[name], M.S.
[name], M.S.
[name], M.S.
[name], B.S.
[name], B.S.

3. Abstract:

The current study will investigate methods for enhancing cognitive training (CT) effects in healthy older adults by employing a combination of interventions facilitating neural plasticity and optimizing readiness for learning. Adults over the age of 65 represent the fastest growing group in the US population. As such, age-related cognitive decline represents a major concern for public health. Recent research suggests that cognitive training in older adults can improve cognitive performance, with effects lasting up to 10 years. However, these effects are typically limited to the tasks trained, with little transfer to other cognitive abilities or everyday skills. A pilot randomized clinical trial will examine the individual and combined impact of pairing cognitive training with transcranial direct current stimulation (tDCS). tDCS is a method of non-invasive brain stimulation that directly stimulates brain regions involved in active cognitive function and enhances neural plasticity when paired with a training task. We will compare changes in cognitive and brain function resulting from CT combined with active tDCS versus CT combined with sham tDCS using a comprehensive neurocognitive, clinical, and multimodal neuroimaging assessment of brain structure, function, and metabolic state. A precision dosing algorithm will be used to determine the appropriate levels of current and location of electrodes to deliver current using tDCS. Functional magnetic resonance imaging (fMRI) will be used to assess brain response during working memory, attention, and memory encoding; the active cognitive abilities trained by CT. Proton magnetic

resonance spectroscopy (MRS) will assess cerebral metabolites, including GABA concentrations sensitive to neural plasticity.

We hypothesize that:

- 1) tDCS will enhance neurocognitive function, brain function, and functional outcomes from CT, with combined CT and tDCS providing the most benefit;

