A randomized clinical trial will enroll 40 participants. Cognitively healthy elderly adults, age 65-89 will undergo either a CT intervention in combination with optimized transcranial direct current brain stimulation (tDCS) or sham tDCS control. The CT intervention will employ a suite of adaptive training tasks from the POSIT Science Brain HQ²⁸¹; a well validated CT method for enhancing cognitive functioning in the elderly. Participants will receive tDCS or sham/placebo precision stimulation administered during training.

Participants will be assessed at baseline and after CT (2 weeks). At each time point, a comprehensive neurocognitive, clinical and multimodal neuroimaging assessment of brain function, metabolic state, and brain structure will be conducted.

FMRI will be used to assess brain response during working memory, attention and memory encoding. Proton magnetic resonance spectroscopy (MRS) will assess cerebral metabolites, including gamma-aminobutyric acid (GABA) concentrations, sensitive to neural plasticity in task-associated brain regions.

The central hypothesis of this proposal is that optimized tDCS will increase neural plasticity in task associated brain regions, facilitating effectiveness of CT and transfer to everyday function.

Aim 1. Determine whether neurocognitive improvement and longer-term functional outcome (as measured by “ecological assessment”) are better when CT is coupled with tDCS, an intervention that will increase neural plasticity and augment training effects.

H1.1. Active tDCS combined with CT will amplify effects of CT on measures of attention, working memory, executive functioning, and learning efficiency, while sham tDCS will not.

H1.2. Active tDCS will enhance near and far transfer of CT, but sham will not evidence near or far transfer.

Aim 2. Determine whether CT combined with tDCS leads to greater functional and metabolic brain changes (fMRI, MRS). Effects will parallel Aim 1.

H2.1. Combined CT + tDCS will potentiate decrease activation in working memory and attentional (dorsolateral prefrontal cortex, medial frontal cortex, inferior parietal lobe, supplementary motor association cortex) brain systems, reflecting increased neural efficiency, while CT + sham tDCS will not.

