H2.2 Cerebral metabolite alterations will occur secondary to CT and tDCS, with long-term increase in GABA and *N*-acetyl aspartate (NAA) concentrations, and decreased choline (Cho) and myoinositol (MI) concentrations in the frontal cortex. CT and tDCS will modulate MRS GABA in frontal areas. These effects will be specific to CT.

Aim 3. Investigate the performance of optimized tDCS compared to conventional application within the literature

H3.1. Optimized tDCS + CT will generate augmented behavioral gains beyond those observed under conventional tDCS application.

H3.2 Optimized tDCS + CT will also demonstrate greater physiological changes of functional connectivity within the working memory network and glutamate/glutamine concentrations within the prefrontal cortex compared to conventional tDCS application.

6. Research Plan:

6.1. Experimental design. This study employs a randomized trial design with 40 participants. One factor with two levels [Factor 1 = stimulation type (active or sham) yields two cells. Thus, participants will be assigned to one of two conditions:

- 1: Active tDCS + CT
- 2: Sham tDCS + CT

CT has previously been established with strong effects on cognitive and functional outcomes. Some small clinical trials showed small to large effects of tDCS in conjunction with CT.

Participants will be assessed at two primary time points during the study, plus one screening visit on the front end to be sure they meet all inclusion criteria for the study:

- 1) Informed Consent and Screening Visit
- 2) Assessment Visit #1- baseline pre-training
- 3) Assessment Visit #2- post-2 weeks

This design will enable longitudinal analyses of CT and tDCS effects. We will examine their effects on cognitive performance, functional and metabolic neuroimaging measures, and everyday functional abilities. At each assessment, we will obtain clinical and medical history, neurocognitive measures, and neuroimaging (structural MRI, fMRI, MRS). All participants will undergo neuroimaging at baseline and following training.

Screening	✓	✓	✓	✓		✓		
Assessment Visits Activity Summary	Informed Consent Form	Medical History	Hearing and Vision Tests	Memory and Thinking Tasks	Physical and Medical Self Reports	MRI Screen-Form	NIH tool box	MRI Brain Scan Appt.
Visit #1 Baseline				✓	✓	✓	✓	✓
Visit #2 After 2 weeks (10 days) of Training				✓	✓	✓	✓	✓
Daily Lab Visits	Brain Training Games	Brain Stimulation/Sham	tDCS Sensation Questions					
Days 1-10	✓	✓	✓					

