6.2. Study participants and randomization procedure. We will recruit 40 older adults (age: 65-89 years). Study participants will consist of healthy individuals who have expressed an interest in taking part in an intervention aimed at optimizing and possibly preserving cognitive functioning and brain health. We will use web-based permuted block randomization to randomly divide participants into the two groups. People with pre-existing dementia, neurological brain disease, or meet criteria for a diagnosis of mild cognitive impairment (MCI) will be excluded, though people with subjective concerns about their cognitive functioning, who do not meet these criteria, may participate. Detailed inclusion/exclusion criteria can be found in Section 7.

6.2.1. Experimental Design Considerations and Limitations: CT Approach. The POSITScience BrainHQ treatment program was selected because it 1) provides specific training tasks directed at three essential cognitive domains tied to our aims and hypotheses (attention, working memory, executive control) that correspond with the neurocognitive and functional neuroimaging measures to be studied; (2) is shown to produce significant cognitive and functional improvements with good effect sizes in past RCTs (ACTIVE) with up to 10 year durability and transfer of training to measures of self-reported everyday functioning; 3) provides a “cognitive treatment engine²⁸²” which alone has a very high likelihood of yielding significant cognitive and functional

improvements, enabling us to test the augmenting effects of tDCS; and 4) is computerized, well standardized, and efficiently implemented.

Combined CT. We selected a combined CT approach rather than testing one specific training task: 1) This would optimize CT treatment effects for this primary intervention, providing a strong and reliable engine of change with which to examine effects of tDCS; 2) This approach enables us to affect several related cognitive functions that are strongly dependent on neural plasticity of the frontal cortex; and 3) This approach would maximize participants interest and motivation versus a single task that could become boring.

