Neuroimaging measures. We will focus on functional (fMRI) and cerebral metabolic (proton MRS) indices for two reasons: 1) These modalities are most linked to and likely sensitive to CT-associated neural plasticity and brain changes; and 2) Changes in these domains are likely to occur over the course of training compared to structural neuroimaging measures. We include active fMRI tasks related to the cognitive functions to be trained, as well as a passive resting state condition to examine the DMN. With respect to MRS, we use a single voxel method to achieve optimal sensitivity and will measure from one ROI (frontal). Along with Creatine (Cr), we will examine cerebral metabolites sensitive to neuronal loss and membrane disturbances (NAA, GLx), and pro-inflammatory processes (Ch, MI). We will also measure cerebral GABA concentrations using a state-of-the-art MRS approach that will reflect neural plasticity in ROIs. The MRS indices will be examined for Aims 2. We will also collect FLAIR imaging data to assess white matter hyperintensity load, as a possible predictor of treatment response (secondary aim)

6.3. Procedural sequence. The sequence and flow of the assessments to be conducted at baseline and each subsequent assessment is shown below. We describe participant recruitment and retention strategies in the Human Subjects section. We will inform potential participants about the study, and obtain their consent. We will then screen for inclusion/exclusion criteria and schedule them for baseline assessment visit #1 evaluation. All

[figure not shown]
following assessments are identical otherwise.

6.4 Cognitive Training. CT will involve up to 10 hours of training over 2-weeks (10 days). At the screening visit and post 2-week intervention participants will complete a 20-minute composite measure of the cognitive training tasks. *Training platform.* CT employs a PositScience BrainHQ suite via its researcher portal. These tasks are web-based and multi-platform (i.e., Windows, Mac). Participants will be randomly assigned to training on 4 tasks focusing on working memory or 4 tasks focusing on attention/speed of processing. Participants will be required to have a specific viewing distances. Study interventionists will provide daily performance summaries. The rationale and task demands for each component were described earlier (A.3.3). These CT are

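### The plan says only that changes will be compared and names no model; prespecify adjustment of each post-training outcome for its own pre-training value

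*Combined protocol and SAP*

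**What the plan says.** The Abstract (section 3) states the comparison: "We will compare changes in cognitive and brain function resulting from CT combined with active tDCS versus CT combined with sham tDCS". Section 6.1 adds only that "This design will enable longitudinal analyses of CT and tDCS effects". There is no statistical analysis section. The one analysis coefficient mentioned is for electrode placement error (section 6.5); no baseline value of any outcome is named as a covariate.

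On design, section 6.1 says "This study employs a randomized trial design with 40 participants", and section 6.2 says "We will use web-based permuted block randomization to randomly divide participants into the two groups"; the allocation ratio is not given. Sections 5 and 6.1 provide one assessment before training and one after 2 weeks. The cognitive battery is listed at both visits, and for imaging section 6.1 says "All participants will undergo neuroimaging at baseline and following training".

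The POSIT composite of the training tasks is less clear. Section 6.4 says "At the screening visit and post 2-week intervention participants will complete a 20-minute composite measure of the cognitive training tasks". The visit list in section 6.7 also places the pre-training composite at screening and does not name it under the assessment visits. The table in section 6.2.1 lists a Posit measure at screening and again at the baseline and post assessments. Section 7 uses the POSIT screening tasks to limit entry to working memory at or below the 75th percentile.

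**The concern.** With one pre and one post value and randomised arms, the analyst must choose how much of the baseline to subtract. A raw change score fixes the slope on baseline at 1. A baseline-adjusted model estimates the slope from the data. Where the best slope is well below 1, raw change carries avoidable baseline noise into the arm difference and over-corrects when the arms happen to start apart.

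Two things are at stake. One is precision in a trial of 40 for which no power calculation is given. The other is that two legitimate analyses give different answers on the same data. With many cognitive and imaging outcomes, leaving the choice open until the data are seen allows it to be made outcome by outcome.

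**Working it through.** The plan states no SD, pre-post correlation, alpha, power or target effect, so it has no figure to reproduce. The calculation below is conditional.

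**Inputs.** From the documents: total N = 40, two randomised arms, one pre and one post value. Assumed: 1:1 allocation (n = 20 per arm), two-sided alpha 0.05, no dropout, correlation rho from 0.3 to 0.8, and k = SD(post)/SD(pre), first set to 1. The pre SD is 1.

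**Formulas, per-person variance.**
- Raw change: 1 + k² − 2·rho·k.
- Baseline-adjusted: k²(1 − rho²), with optimal slope rho·k.
- Difference: (1 − rho·k)². This cannot be negative, so adjustment is never worse in large samples. The gain is zero only when rho·k = 1.
- With k = 1: 2(1 − rho) against 1 − rho², a reduction of (1 − rho)/2.
- At N = 40, estimating the slope multiplies the adjusted variance by 1 + 1/(N − 4) = 1 + 1/36 = 1.028.

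**Results with k = 1.** The variance of an arm difference is 2/20 = 0.1 times the per-person variance. Power is from the t distribution (38 df for change, 37 df adjusted), with slope estimation charged to the adjusted model.

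| rho | Reduction, large N | Reduction, N = 40 | Power for 0.8 SD: change → adjusted | Detectable effect at 80% power, SD |
|---|---|---|---|---|
| 0.3 | 35% | 33% | 55% → 72% | 1.08 → 0.88 |
| 0.5 | 25% | 23% | 69% → 80% | 0.91 → 0.80 |
| 0.8 | 10% | 7.5% | 97% → 98% | 0.57 → 0.55 |

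A simulation of 40,000 trials per value of rho gave reductions of 33.5%, 22.5% and 7.2% at N = 40. At rho = 0.5 the adjusted variance is 0.1 × 0.75 × 1.028 = 0.0771 against 0.1 for raw change, so the trial performs as if it had 20 × 0.1/0.0771 = 26 per arm. At rho = 0.95 the gain at N = 40 is about zero.

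**Unequal SDs (large N).** With k = 0.8 the reduction is 50%, 43% and 36% at rho 0.3, 0.5 and 0.8. With k = 1.25 it is 22%, 11% and 0%; at rho = 0.8 the slope is 0.8 × 1.25 = 1.

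**Range-restricted POSIT screening score.** Suppose a bivariate normal pair with the screening value cut off above its 75th percentile (an illustration). The screening variance falls to 0.535. The reduction is 0.535(1 − rho)² / [0.535(1 − rho)² + 1 − rho²] = 22%, 15% and 6% at rho 0.3, 0.5 and 0.8, or about 20%, 13% and 3% at N = 40.

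**Chance imbalance.** The SD of the baseline difference is √(2/20) = 0.32, so a gap of at least 0.3 SD in either direction arises in about 34% of such trials. At rho = 0.5 and k = 1, a gap of 0.32 SD moves the raw-change contrast by (1 − 0.5) × 0.32 = 0.16 SD towards the arm that started lower. This is the same loss seen another way: 0.16² ≈ 0.025 = 0.1 − 0.075.

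**The case against.** The strongest reply is that the plan never commits to subtracting pre from post. The sentence in the Abstract says what will be compared, not how; adjusted models are often described as comparing change, and the longitudinal analyses promised in section 6.1 could include one. This stands. A reader might infer that the protocol has chosen an inefficient analysis. The documents support only that no model is specified and that raw change is permitted.

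Three further limits also stand.
- The gain is not a property of this trial. It depends on an assumed correlation and on equal SDs. The best slope is rho × SD(post)/SD(pre), so it cannot be said to lie below 1 for every outcome.
- Raw change is unbiased over randomisation. The 0.16 SD shift is conditional on an imbalance and already counted in the variance, so it is not a second harm.
- A reader might expect the loss to be greatest for the MRS and fMRI outcomes of Aim 2. The documents give no reliability figure for any outcome, so this is unsupported.

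The study describes itself as a pilot and as exploratory and makes no power claim. That lowers the stakes but is no reason to leave the estimator open when the better choice uses data already planned.

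**Conclusion.** The point holds as a gap in specification with a nearly free improvement, not as an error in a stated analysis. Under randomisation, adjustment for the outcome's own pre-training value is asymptotically never less precise than raw change. With equal SDs and rho between 0.3 and 0.8 the variance of the arm difference falls by 10 to 35%, or about 7 to 33% at 20 per arm. At rho = 0.5, power for a 0.8 SD effect rises from about 69% to 80%. The assumptions are rho, equal SDs, 1:1 allocation, two-sided 0.05 and no dropout; none is stated in the documents. The gain is smaller where the post SD moderately exceeds the pre SD, as is plausible for the range-restricted POSIT screening score. It disappears where rho × SD(post)/SD(pre) equals 1, and at this sample size when rho is near 0.95 with equal SDs.

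**What to change.** Add to the analysis text: each active-versus-sham comparison in Aims 1 and 2 for an outcome with a pre and a post value is the arm coefficient in a linear model of the post-training value, with that outcome's own pre-training value as covariate, or the equivalent longitudinal model with a common baseline mean. Report raw change descriptively.

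For the POSIT composite, first reconcile sections 6.2.1, 6.4 and 6.7 on whether the pre-training value is taken at screening or at Visit 1, and name that value as the covariate. The functional outcome in Aim 1 has no evident instrument in the visit lists, so the rule can apply to it only once a measure with a pre-training value is identified.

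The cost is one sentence plus that reconciliation, and one degree of freedom per model. No new data are needed. Make the change before any analysis by arm.

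### Every participant receives CT, so the effect of CT itself, the effect of tDCS without CT, and H2.2's claim of specificity to CT cannot be estimated; only active versus sham tDCS given CT can

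*Combined protocol and SAP*

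**What the plan says.** Section 6.1 (Experimental design) sets out the randomised structure: "One factor with two levels [Factor 1 = stimulation type (active or sham) yields two cells". It continues, "Thus, participants will be assigned to one of two conditions", and lists active tDCS + CT and sham tDCS + CT. Assessments are at baseline and after two weeks, with 40 participants in total. The same section says that the design allows longitudinal analyses of the effects of both CT and tDCS.

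The aims reach further than that structure:

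- Section 5, H2.2: "Cerebral metabolite alterations will occur secondary to CT and tDCS", with predicted directions for GABA, NAA, choline and myo-inositol in frontal cortex. It ends: "These effects will be specific to CT".
- Section 3 (Abstract): the pilot trial "will examine the individual and combined impact of pairing cognitive training with transcranial direct current stimulation (tDCS"). Hypothesis 1 adds "with combined CT and tDCS providing the most benefit".
- The abstract then describes the planned comparison as change "resulting from CT combined with active tDCS versus CT combined with sham tDCS".

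Two other places bear on the point. Section 6.4 randomly assigns participants to working-memory tasks or to attention/speed tasks, an allocation that section 6.1 does not mention. Section 6.6.2 acquires the GABA-edited spectra from one medial frontal voxel. The document has no statistical analysis section that defines specificity to CT or gives a test for H2.2.

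**The concern.** A claim that a change is due to CT, or specific to CT, needs people who did not receive CT. A claim about the individual impact of tDCS needs people who received tDCS without CT. The trial has neither group. With two assessments, the only CT analysis that the longitudinal sentence in section 6.1 can deliver is pre-post change within an arm. That change contains whatever else happens over two weeks: retest practice on the cognitive tests, passage of time, and scanner or spectroscopy drift. With a single voxel there is also no control region within the person.

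At stake is what the trial may report. Section 8 says that the data will be a foundation for larger studies. If within-arm change is written up as a CT effect on metabolites or cognition, those studies would inherit an attribution that this trial did not test. The point is separate from the missing conventional-tDCS comparator in Aim 3: adding that comparator would leave the CT claims where they are.

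**Working it through.** **Inputs.** Two cells, both with CT, and N = 40 with visits at baseline and two weeks (section 6.1); two groups by permuted blocks, ratio not stated (section 6.2). I assume 1:1, so 20 per arm. The documents give no alpha, power, effect size, SD or dropout, so there is no figure of the plan's own to reproduce.

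**Step 1: what the two cells identify.** Write the mean outcome as b0 + b1·CT + b2·tDCS + b3·CT·tDCS, with CT and tDCS coded 0 or 1.

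- Active + CT: b0 + b1 + b2 + b3
- Sham + CT: b0 + b1
- Difference: b2 + b3, the effect of active over sham tDCS given CT

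Two cells give a design matrix of rank 2 for four parameters.

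| Effect | Parameter | Estimable with the planned cells? |
|---|---|---|
| tDCS added to CT | b2 + b3 | Yes |
| CT alone | b1 | No |
| tDCS without CT | b2 | No |
| CT + tDCS versus neither | b1 + b2 + b3 | No |
| CT × tDCS interaction | b3 | No |

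**Step 2: whether the baseline visit rescues the CT effect.** Add a period term p for everything other than CT and tDCS that changes over two weeks.

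- Sham arm change: p + b1
- Active arm change: p + b1 + (b2 + b3)

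The period and CT columns are identical, because everyone is untrained at baseline and trained at Visit 2. The matrix (intercept, period, CT, tDCS given CT) has rank 3 of 4. Only the sum p + b1 and the active-minus-sham difference can be estimated. CT is fully aliased with period. For tDCS without CT the position is weaker still, since no participant contributes even pre-post data.

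**Step 3: whether section 6.4 supplies a control.** Both task sets are CT, so CT = 1 for everyone. That randomisation could compare training content (about 20 versus 20 if balanced, or 10 per cell when crossed with stimulation). It cannot compare CT with no CT.

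**Step 4: illustration of false attribution.** Assume a true CT effect of zero, a non-CT shift of d SDs of change, and a two-sided 5% paired t-test in one arm of n = 20. The critical value is t(0.975, 19) = 2.093 and the non-centrality is d·√20.

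| Assumed shift d | d·√20 | P(significant change) |
|---|---|---|
| 0.1 | 0.447 | 0.07 |
| 0.2 | 0.894 | 0.14 |
| 0.3 | 1.342 | 0.25 |
| 0.4 | 1.789 | 0.40 |
| 0.5 | 2.236 | 0.56 |

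The nominal rate is 0.05.

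**Step 5: what a full 2×2 would offer at the same N.** With CT yes/no crossed with active/sham, the rank is 4 of 4 and every row in the first table becomes estimable. At 10 per cell, two-sided 5%, 80% power, unit SD and a normal approximation, the multiplier is 1.960 + 0.842 = 2.802. The minimum detectable standardised effects are 2.802·√(2/20) = 0.89 for a main effect, 2.802·√(2/10) = 1.25 for a simple effect, and 2.802·√(4/10) = 1.77 for the interaction.

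**The case against.** The strongest defence is that this is a deliberate add-on design, openly described. The abstract names the active-versus-sham comparison, the central hypothesis and Aims 1 and 2 concern tDCS added to CT, and section 6.2.1 explains that CT was chosen as a reliable background against which to test tDCS. The trial is a pilot, and the monitoring plan in section 7 calls it exploratory. All of this stands: giving CT to both arms is not itself a fault. It does not remove the claims that go beyond the add-on question. Nor does earlier evidence that CT works supply the contrast missing here; section 6.1 cites that evidence for cognitive and functional outcomes, not metabolites.

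A reader might infer four stronger things that the documents do not support.

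- **That all of H2.2 is untestable.** It is not. The effect of active over sham tDCS on frontal metabolites, given CT, is randomised. What fails is attribution to CT itself and the closing sentence.
- **That hypothesis 1's phrase "with combined CT and tDCS providing the most benefit" has no contrast.** Read against the two arms that the abstract names, it means active + CT over sham + CT, which is testable. Only a four-cell reading, which the abstract does not set out, would defeat it.
- **That active versus sham is the only randomised comparison.** Section 6.4 adds one of training content. It gives no CT-versus-no-CT comparison.
- **That the percentages in step 4 measure bias in this trial.** They do not. The shift, the arm size and the within-arm test are all assumed, and the documents specify no such test. For metabolites, cognitive practice is not an obvious source of shift, and the documents give no drift figure.

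**Conclusion.** The concern holds, limited to three claims: the effect of CT itself, the effect of tDCS without CT, and specificity to CT. With 0 of 40 participants lacking CT, none of these can be estimated. That conclusion follows from the two cells alone and needs no numerical assumption. The range of about 7% to 56% is illustrative and carries all the assumptions of step 4.

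The main randomised question, active versus sham tDCS in people receiving CT, is unaffected for both cognition and metabolites. As written, however, H2.2 and the longitudinal sentence in section 6.1 would lead to uncontrolled two-week change being read as a CT effect, so the wording should be changed before analysis.

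**What to change.** 1. **Section 5, H2.2:** delete the closing sentence on specificity. Restate the hypothesis as the active-minus-sham difference in Visit 2 GABA, NAA, choline and myo-inositol, adjusted for the Visit 1 value.
2. **Section 3:** replace the reference to individual and combined impact with *added effect of active versus sham tDCS in people receiving CT*. Word hypothesis 1 as active tDCS + CT versus sham tDCS + CT.
3. **Section 6.1:** change the longitudinal sentence so that it refers to analyses of the active-versus-sham effect given CT.
4. **Throughout:** state that within-arm change is descriptive only. This also governs the predictions in H1.2 and H2.1 about what the sham arm will not show, which should be read as between-arm differences.
5. **Sections 6.1 and 6.4:** reconcile the one-factor, two-cell description with the second randomisation to training content.

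The cost is rewording: no new arm, participants or data. The claims become narrower. Adding no-CT cells at N = 40 is not the proportionate remedy, since 10 per cell would detect only very large effects (step 5).
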